**Table 5: Safety TLFs**

T/F/L	Title	Population
-------	-------	------------

T	Concomitant medications	miITT
L	Concomitant medications	miITT
T	Treatment exposure and compliance	miITT
L	Treatment exposure and compliance	miITT
T	Dose modifications and interruption	miITT
L	Dose modifications and interruption	miITT
T	Overall summary of TEAEs	Safety
T	TEAEs by Soc/PT	Safety
T	TEAEs by PT	Safety
T	TEAEs by severity and PT	Safety
T	Treatment related AEs by PT	Safety
T	Serious TEAEs by Soc/PT	Safety
T	Serious TEAEs by PT	Safety
T	Treatment related SAEs by PT	Safety
T	Grade 3-5 TEAEs by Soc/PT	Safety
T	Grade 3-5 TEAEs by PT	Safety
T	Treatment related grade 3-5 AEs by Soc/PT	Safety
T	TEAEs leading to Study treatment discontinuation by Preferred Term	Safety
T	Related TEAEs leading to Study treatment discontinuation by Preferred Term	Safety
T	TEAEs leading to dose interruption by Preferred Term	Safety
T	Related TEAEs leading to dose interruption by Preferred Term	Safety
T	TEAEs leading to dose modification by Preferred Term	Safety
T	Related TEAEs leading to dose modification by Preferred Term	Safety
T	TEAEs leading to dose reduction by Preferred Term	Safety
T	Related TEAEs leading to dose reduction by Preferred Term	Safety
L	AEs	Safety
L	AE Leading to treatment discontinuation	Safety
L	Death	Safety
T	Lab values and their change from baseline	Safety
F	Lab values by visit	Safety
T	Shifts in CTC grade from baseline to highest grade post-baseline of laboratory	Safety
L	Lab values with CTC grade $\geq 3$	Safety
T	Vital signs and their change from baseline	Safety
L	Vital signs	Safety
T	ECG parameters and their change from baseline	Safety

F	ECG parameters by visit	Safety
T	Number and percentage of subjects with QTcF by visit a) absolute ranges and b) change from baseline	Safety
T	QTcF abnormalities	Safety
L	ECG values	Safety

## 6 APPENDIX B: Kadmon Algorithmic Response Assessments

For determination of responses and DOR per sponsor assessment, criteria for baseline organ involvement and response assessments are described below.

### Baseline Organ Involvement

Organ	Organ Involvement
Esophagus	NIH Esophagus Score $\geq 1$ , not entirely explained by non-cGVHD cause
Upper GI	NIH Upper GI Score $\geq 1$ , not entirely explained by non-cGVHD cause
Lower GI	NIH Lower GI Score $\geq 1$ , not entirely explained by non-cGVHD cause
Lungs	FEV1 <75% predicted, not entirely explained by non-cGVHD cause If no PFTs available, use NIH lung score $\geq 1$ , not entirely explained by non-cGVHD cause
Eyes	NIH Eye Score $\geq 1$ , not entirely explained by non-cGVHD cause
Joints and Fascia	P-ROM Score <25 (< maximal score) or NIH Joints/Fascia Score $\geq 1$ , not entirely explained by non-cGVHD cause
Skin	NIH Skin Score $\geq 1$ , not entirely explained by non-cGVHD cause
Mouth	NIH Modified Oral Mucosal Rating Score $\geq 1$ , not entirely explained by non-cGVHD cause
Liver	Elevation $> 2x$ ULN of one or more (ALT, ALP, Total Bilirubin), not entirely explained by non-cGVHD cause

## Response Assessments

Organ	Complete Response	Partial Response	Unchanged	Progression	Non Evaluable
Esophagus	NIH Esophagus Score 0 after previous involvement	Decrease in NIH Esophagus Score by 1 or more points	No change or increase from 0 to 1 in NIH Esophagus Score	Increase in NIH Esophagus Score by 1 or more points, except 0 to 1	NIH esophagus score is Non evaluable
Upper GI	NIH Upper GI Score 0 after previous involvement	Decrease in NIH Upper GI Score by 1 or more points	No change or increase from 0 to 1 in NIH Upper GI Score	Increase in Upper GI Score by 1 or more points, except 0 to 1	NIH upper GI score is Non evaluable
Lower GI	NIH Lower GI Score 0 after previous involvement	Decrease in NIH Lower GI Score by 1 or more points	No change or increase from 0 to 1 in NIH Lower GI Score	Increase in Lower GI Score by 1 or more points, except 0 to 1	If NIH Lower GI score is Non evaluable
Lungs	%FEV1 $\geq$ 80% after previous involvement; or NIH Lung Symptom Score 0 after previous involvement if PFTs not available	Increase by 10% absolute value of %FEV1; or decrease in NIH Lung Symptom Score by 1 or more points if PTSs not available	Not in the other categories	Decrease by 10% absolute value of %FEV1 and %FEV1 $<$ 75%; or increase in NIH Lung Symptom Score by 1 or more points, except 0 to 1 if PFTs not available	NIH Lung score is Non evaluable and %FEV1 is missing
Eyes	NIH Eye Score 0 after previous involvement	Decrease in NIH Eye Score by 1 or more points	No change or increase from 0 to 1 in NIH Eye Score	Increase in NIH Eye Score by 1 or more points, except 0 to 1	NIH eye score is Non evaluable
Joints and Fascia	NIH Joint and Fascia Score 0 and P-ROM score 25 after previous	Decrease in NIH Joint and Fascia Score by 1 or more points or increase in P-	Not in the other categories	Increase in NIH Joint and Fascia Score by 1 or more points or decrease in P-	Both in NIH Joint and Fascia and P-ROM scores are Non

Organ	Complete Response	Partial Response	Unchanged	Progression	Non Evaluable
	involvement in at least one measure	ROM score by 1 or more points for any site		ROM score by 1 or more points for any site	evaluable
Skin	NIH Skin Score 0 after previous involvement	Decrease in NIH Skin Score from baseline by 1 or more points	No change or increase from 0 to 1 in NIH Skin Score	Increase in NIH Skin Score from baseline by 1 or more points, except 0 to 1	NIH skin score is Non evaluable
Mouth	NIH Modified OMRS 0 after previous involvement	Decrease in NIH Modified Oral Mucosa Rating Score of 2 or more points	No change in NIH Modified Oral Mucosa Rating Score	Increase in NIH Modified Oral Mucosa Rating Score of 2 or more points	NIH mouth score is Non evaluable
Liver	Normal ALT, ALP and total bilirubin after elevation of one or more at baseline	50% improvement in ALT, ALP, or total bilirubin without increase by 2x ULN for any other parameters of ALT, ALP or total bilirubin	Not in the other categories	Increase by 2x ULN for any one of ALT, ALP or total bilirubin	If ALT, ALP and total bilirubin are missing
Global	GSR 0	GSR decreases by 2 or more points	Not in the other categories	GSR increases by 2 or more points	Not applicable

Organs not involved at baseline can progress according to the definitions in this Response Assessments table, but cannot achieve a response (PR or CR).

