5.3 TREATMENT ASSIGNMENT

Eligible participants will be randomized and assigned to a treatment arm (A or B) in this open label, randomized study in accordance with the randomization schedule.

Randomization will be stratified according to:

- Prior ibrutinib therapy (yes/no).
- Severe cGVHD (yes/no) where severe cGVHD is defined as at least one organ with a score of 3, or a lung score of 2 or 3 ([Table 1](#)) ([26](#)).

The randomization will be a block randomization with a block size of 4.

Table 1 - cGVHD Severity Definitions

cGVHD Severity	Definition
Mild cGVHD	1 or 2 organs involved with no more than score 1 plus Lung score 0
Moderate cGVHD	3 or more organs involved with no more than score 1 OR At least 1 organ (not lung) with a score of 2 OR Lung score 1
Severe cGVHD	At least 1 organ with a score of 3 OR Lung score of 2 or 3

Key points:

1. In skin: higher of the two scores to be used for calculating global severity.
2. In lung: FEV₁ is used instead of clinical score for calculating global severity.
3. If the entire abnormality in an organ is noted to be unequivocally explained by a non-GVHD documented cause, that organ is not included for calculation of the global severity.
4. If the abnormality in an organ is attributed to multifactorial causes (GVHD plus other causes) the scored organ will be used for calculation of the global severity regardless of the contributing causes (no downgrading of organ severity score).

Reference: Jagasia et al. ([26](#))

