21.2 APPENDIX B: CGVHD ACTIVITY ASSESSMENT FOR CLINICIAN

	SCORE 0	SCORE 1	SCORE 2	SCORE 3
ESOPHAGUS	No esophageal symptoms	Occasional dysphagia or odynophagia with solid food or pills during the past week	Intermittent dysphagia or odynophagia with solid foods or pills, but not for liquids or soft foods, during the past week	Dysphagia or odynophagia for almost all oral intake, on almost every day of the past week
				
 Abnormality present but explained entirely by non-GVHD documented cause (specify): _____				
 Abnormality thought to represent GVHD PLUS other causes (specify): _____				
UPPER GI	No symptoms	Mild, occasional symptoms, with little reduction in oral intake during the past week	Moderate, intermittent symptoms, with some reduction in oral intake during the past week	More severe or persistent symptoms throughout the day, with marked reduction in oral intake, on almost every day of the past week
				
 Abnormality present but explained entirely by non-GVHD documented cause (specify): _____				
 Abnormality thought to represent GVHD PLUS other causes (specify): _____				
LOWER GI	No loose or liquid stools during the past week	Occasional loose or liquid stools, on some days during the past week	Intermittent loose or liquid stools throughout the day, on almost every day of the past week , without requiring intervention to prevent or correct volume depletion	Voluminous diarrhea a on almost every day of the past week, requiring intervention to prevent or correct volume depletion
				
 Abnormality present but explained entirely by non-GVHD documented cause (specify): _____				
 Abnormality thought to represent GVHD PLUS other causes (specify): _____				

	SCORE 0	SCORE 1	SCORE 2	SCORE 3
LUNGS	No symptoms	Mild symptoms (shortness of breath after climbing one flight of steps)	Moderate symptoms (shortness of breath after walking on flat ground)	Severe symptoms (shortness of breath at rest; requiring O ₂)

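### KARA disregards wholly non-cGVHD abnormalities at baseline but can score them as cGVHD progression afterwards, which mainly affects exploratory KARA duration of response

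*SAP*

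**What the plan says.** SAP Appendix B has two tables. In Baseline Organ Involvement, each of the nine organ rows carries the condition "not entirely explained by non-cGVHD cause". In Response Assessments, progression depends only on the change in a score, FEV1, P-ROM or a laboratory value. The lower GI cell reads "Increase in Lower GI Score by 1 or more points, except 0 to 1" and the liver cell reads "Increase by 2x ULN for any one of ALT, ALP or total bilirubin". Neither these cells nor any other cell of that table mentions cause. A note below it adds that "Organs not involved at baseline can progress according to the definitions in this Response Assessments table", although such organs cannot respond.

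There is a Non Evaluable column, with entries such as "If NIH Lower GI score is Non evaluable". It is not tied to attribution.

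The clinician activity form (Protocol 21.2, Appendix B) has, for each organ, a box labelled "Abnormality present but explained entirely by non-GVHD documented cause (specify", followed by a blank. A second box marks abnormalities thought to be GVHD together with other causes. The Global Severity Rating has neither box. The form is completed at baseline, at on-treatment response visits and at end of treatment (Protocol 6.2.2, 6.2.4 and 6.2.5, and Table 6).

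SAP 3.8.3.2 repeats the ORR and DOR analyses with KARA as an exploratory endpoint and examines concordance with the investigator.

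**The concern.** An algorithm does only what its table says. If cause matters when deciding whether an organ has cGVHD at baseline, it should matter when deciding whether that organ's cGVHD has worsened. As written, a worsening that the site documents as having nothing to do with GVHD is still read as cGVHD progression.

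Such events are foreseeable: SAP 3.11.2 already singles out hepatic events and bacterial, viral and fungal infections for separate summary. At stake is whether the KARA DOR curve measures loss of cGVHD response or a mixture of that and intercurrent illness.

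**Working it through.** The plan states no figure on this point, so the check compares the two tables and traces the consequence. A short illustration of scale follows.

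**Count of rows carrying the exclusion (SAP Appendix B)**

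| Table | Organ rows with the exclusion |
|---|---|
| Baseline Organ Involvement | 9 of 9 |
| Response Assessments | 0 of 9 (0 of 10 with Global) |

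**Case 1: an organ that was clear at baseline.**
- Baseline: skin 2, lower GI 0.
- Cycle 3 Day 1: skin 1, lower GI 0. Skin is PR, and overall is PR.
- Cycle 5 Day 1: skin still 1, lower GI 2, with the box ticked for infectious diarrhoea. A rise from 0 to 2 is not exempt, so lower GI is Progression. By SAP Table 2 the overall response is LR-M, which the table treats as progression.
- DOR under the primary definition (deterioration from best response) and the secondary definition (first lack of response) ends here, at 2 cycles x 28 days = 56 days, although the skin response continues.

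**Case 2: an organ excluded at baseline for the same cause.**
- Baseline lower GI is 1, wholly non-cGVHD, so KARA calls it not involved.
- The same cause later takes it to 2. Only a rise from 0 to 1 is exempt, and the note allows uninvolved organs to progress. KARA scores cGVHD progression in an abnormality it had itself ruled not to be cGVHD.

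**Does Non Evaluable prevent this?** No. Liver is Non Evaluable only when ALT, ALP and total bilirubin are missing. Lung needs a non-evaluable score and a missing %FEV1. For the scored organs the term is undefined and not linked to the box.

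**Which rules filter events?**
- A rise from 0 to 1 is exempt for esophagus, upper and lower GI, eyes, skin and the lung symptom score.
- FEV1 progression needs a fall of 10 points and a value below 75%.
- Mouth needs 2 points, and liver needs an increase of 2x ULN.
- Joints and fascia have no exemption.

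**Scale (illustration only).** Let q be the assumed chance, per assessment, of a wholly non-cGVHD worsening that meets a Progression rule. Take visits as independent.

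The chance that a response meets at least one such event in k later assessments is 1 - (1 - q)^k. On the Protocol 3.1 schedule (Day 1 of Cycles 2, 3, 4, 5, 7, 9, 11 and so on), the last participant enrolled has five assessments by week 24, shortly before the 6-month analysis, so at most k = 4 after a first response. By week 48, before the 12-month analysis, there are eight, so at most k = 7.

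| q | k = 4 | k = 7 |
|---|---|---|
| 1% | 1 - 0.99^4 = 3.9% | 1 - 0.99^7 = 6.8% |
| 2% | 1 - 0.98^4 = 7.8% | 1 - 0.98^7 = 13.2% |
| 5% | 1 - 0.95^4 = 18.5% | 1 - 0.95^7 = 30.2% |

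For ORR, a participant with m visits that would show a response is lost only if every one of them is hit, with chance q^m. With m = 1 this is 1% to 5%. With m = 2 it is 0.01% to 0.25%. DOR is therefore much more exposed than ORR.

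**The case against.** **KARA follows the protocol's own criteria.** The strongest reply is that the response criteria in Protocol Appendix C contain no attribution exclusion either, and that KARA reproduces their lower GI rule almost word for word. This stands, and it rules out a tempting inference: that investigators discount ticked organs, so that KARA creates false disagreement in the concordance table. No text tells investigators to do so when assigning response. The one protocol rule that drops such organs, "If the entire abnormality in an organ is noted to be unequivocally explained by a non-GVHD documented cause, that organ is not included", concerns global severity staging. It is an analogy, not a response rule. It does not, however, explain why KARA applies the exclusion at baseline and then abandons it.

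**The literal rule is conservative.** In an open-label study, a post-baseline flag is a judgement that could erase progression, and excluding flagged organs could only raise KARA ORR and DOR. That is a real cost. But KARA already runs largely on open-label investigator scores and already accepts the same attribution at baseline. Reporting both versions shows the effect of the flag.

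**The reach is narrow.** A reader might infer that every DOR definition is cut short. The tertiary definition counts only new systemic therapy or death, so it is untouched. The quaternary definition sums episodes and resumes after a transient lack of response. ORR accepts a response at any post-baseline assessment (SAP 3.8.1). All of this stands.

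**Conclusion.** The inconsistency within SAP Appendix B is real: attribution is used to define involvement and ignored when scoring progression, so a wholly non-cGVHD worsening counts as cGVHD progression. The effect is confined to the exploratory KARA analyses, mainly primary- and secondary-definition DOR. KARA ORR is affected only when no other visit shows a response.

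It would be wrong to infer a threat to the trial's main result. The primary ORR is investigator-assessed and alone carries alpha, so the primary test and its power do not change.

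The documents give no frequency. The illustrated 3.9% to 18.5% over four later assessments rests on an assumed q of 1% to 5%, constant and independent between visits. It also ignores responses that end earlier through genuine progression, new therapy or death, so the share of DOR values actually altered would be smaller for a given q.

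**What to change.** Add to SAP Appendix B:

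- At a post-baseline visit, an organ flagged on the activity form as wholly explained by a documented non-GVHD cause is not scored as Progression at that visit.
- If that organ was involved at baseline and has not resolved, score it Unchanged. Otherwise leave it out. Simply calling it Non Evaluable and using the remaining organs could allow an overall CR with an involved organ unresolved, against SAP Table 2.
- Continue to score organs marked as GVHD together with other causes.
- Leave the Global row as written, since it has no attribution box. A rise of 2 or more in that rating at the same visit will still count as progression.
- List every visit where the rule is applied, and report KARA ORR and DOR under the current literal rule as a sensitivity analysis.

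The cost is a short SAP paragraph, a small programming change, one listing and a repeat of existing KARA outputs. No new data are needed. The drawback is reliance on an open-label investigator flag that can only remove progressions. The listing and the sensitivity analysis make its influence visible.

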4.3 INCLUSION CRITERIA

GVHD Criteria

1. Male and female participants at least 12 years of age who have had allogeneic hematopoietic cell transplant (HCT).
2. Previously received at least 2 and not more than 5 lines of systemic therapy for cGVHD.
3. Participant has been on a stable dose / regimen of systemic cGVHD treatments for at least 2 weeks prior to screening. Note: Concomitant corticosteroids, calcineurin inhibitors, sirolimus, MMF, methotrexate, rituximab, and extracorporeal photopheresis (ECP) are acceptable. Systemic investigational GVHD treatments are not permitted.
4. Have persistent cGVHD manifestations and systemic therapy is indicated.
5. Karnofsky (if aged ≥ 16 years) / Lansky (if aged < 16 years) Performance Score of ≥ 60 .

Laboratory Parameters

6. Absolute neutrophil count $\geq 1.5 \times 10^9/L$.
7. Platelet count $\geq 50 \times 10^9/L$ with no transfusions within 72 hours.
8. ALT and AST $\leq 3 \times ULN$ ($\leq 5 \times ULN$ if due to cGVHD).
9. Total bilirubin $\leq 1.5 \times ULN$.

10. Glomerular filtration rate (GFR) ≥ 30 mL/min/1.73 m² using the MDRD-4 variable formula (if aged ≥ 18 years) or using the Bedside Schwartz formula (if aged < 18 years).

General Criteria

11. I11 is no longer applicable per amended protocol 05.
12. I12 is no longer applicable per amended protocol 05.
13. I13 is no longer applicable per amended protocol 05.
14. Participant (or the participant's legally authorized representative) is able to provide written informed consent / assent prior to the performance of any study-specific procedures.
15. Weight ≥ 40 kg.
16. It is in the best interest of the participant to participate in the study.

Sex, contraceptive/barrier method and pregnancy testing requirements/breastfeeding

17. All

Contraceptive use by men and women should be consistent with local regulations regarding the methods of contraception for those participating in clinical studies.

• Male participants

Male participants are eligible to participate if they agree to the following during the study intervention period and for at least 90 days after the last administration of study intervention:

- Refrain from donating sperm or cryopreserving sperm;
PLUS, either:
- Be abstinent from heterosexual intercourse as their preferred and usual lifestyle (abstinent on a long term and persistent basis) and agree to remain abstinent;
OR
- Must agree to use contraception/barrier as detailed below:

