21.3 APPENDIX C: CGVHD RESPONSE ASSESSMENT

[figure not shown]
Response Determination for Chronic GVHD Clinical Trials based on Clinician Assessments

Organ	Complete Response	Partial Response	Progression
Skin	NIH Skin Score 0 after previous involvement	Decrease in NIH Skin Score by 1 or more points	Increase in NIH Skin Score by 1 or more points, except 0 to 1
Eyes	NIH Eye Score 0 after previous involvement	Decrease in NIH Eye Score by 1 or more points	Increase in NIH Eye Score by 1 or more points, except 0 to 1
Mouth	NIH Modified OMRS 0 after previous involvement	Decrease in NIH Modified OMRS of 2 or more points	Increase in NIH Modified OMRS of 2 or more points
Esophagus	NIH Esophagus Score 0 after previous involvement	Decrease in NIH Esophagus Score by 1 or more points	Increase in NIH Esophagus Score by 1 or more points, except 0 to 1
Upper GI	NIH Upper GI Score 0 after previous involvement	Decrease in NIH Upper GI Score by 1 or more points	Increase in NIH Upper GI Score by 1 or more points, except 0 to 1
Lower GI	NIH Lower GI Score 0 after previous involvement	Decrease in NIH Lower GI Score by 1 or more points	Increase in NIH Lower GI Score by 1 or more points, except from 0 to 1
Liver	Normal ALT, alkaline phosphatase, and Total bilirubin after previous elevation of 1 or more	Decrease by 50%	Increase by 2 × ULN
Lungs	- Normal %FEV1 after previous involvement - If PFTs not available, NIH Lung Symptom Score 0 after previous involvement	- Increase by 10% predicted absolute value of %FEV1 - If PFTs not available, decrease in NIH Lung Symptom Score by 1 or more points	- Decrease by 10% predicted absolute value of %FEV1 - If PFTs not available, increase in NIH Lung Symptom Score by 1 or more points, except 0 to 1
Joints and fascia	Both NIH Joint and Fascia Score 0 and P-ROM score 25 after previous involvement by at least 1 measure	Decrease in NIH Joint and Fascia Score by 1 or more points or increase in P-ROM score by 1 point for any site	Increase in NIH Joint and Fascia Score by 1 or more points or decrease in P-ROM score by 1 point for any site
Global	Clinician overall severity score 0	Clinician overall severity score decreases by 2 or more points on a 0-10 scale	Clinician overall severity score increases by 2 or more points on a 0-10 scale

ULN indicates upper limit of normal.

Abstracted from: Lee SJ, Wolff D, Kitko C, et al. *Biol Blood Marrow Transplant* 2015; 21:984 – 999.

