### **3.8.3.2 ORR using Kadmon Algorithmic Response Assessment (KARA)**

In addition to ORR assessed by investigators, the sponsor will conduct response assessments according to criteria listed in Appendix B for each individual organ, then assign overall response according to [Table 2](#) (cGVHD response definitions). Analyses of ORR and DOR will be repeated with this sponsor assessment of overall response.

Concordance with investigator determined responses will be analyzed.

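### The KARA liver rule lets a 50% fall in an analyte that was normal at baseline count as liver PR; the KARA lung progression rule also carries a 75% FEV1 floor that the protocol criteria lack

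*SAP*

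**What the plan says.** **Role of KARA.** SAP 3.8.3.2 places KARA among the exploratory endpoints. The sponsor's algorithm classifies each organ by Appendix B and then assigns overall response by SAP Table 2. "Analyses of ORR and DOR will be repeated with this sponsor assessment of overall response", and concordance with the investigators' responses is analysed. SAP section 3 gives alpha to the primary ORR only, which SAP 3.8.1 defines as investigator-assessed.

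**Liver.** Appendix B counts the liver as involved at baseline if there is elevation above 2x "ULN of one or more (ALT, ALP, Total Bilirubin), not entirely explained by non-cGVHD cause". Liver PR is "50% improvement in ALT, ALP, or total bilirubin without increase by 2x ULN for any other parameters" of the three. Liver progression is an increase by 2x ULN in any one of them. A closing note bars response in an organ not involved at baseline, while allowing such an organ to progress. Protocol Appendix C (section 21.3) gives liver PR only as a 50% decrease and names no analyte.

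**Lungs.** Protocol Appendix C defines progression as "Decrease by 10% predicted absolute value of %FEV1", with no floor. Appendix B has "Decrease by 10% absolute value of %FEV1 and %FEV1" below 75%. Whatever fits no other category is unchanged. KARA lung involvement at baseline is FEV1 below 75% predicted.

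**Entry limits (protocol 4.3).** Bilirubin must be at or below 1.5x ULN. ALT and AST must be at or below 3x ULN, or 5x if due to cGVHD.

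**The concern.** An algorithm does what its text says. The involvement gate works on the organ, while the PR rule works on any one analyte, and nothing links the two. One abnormal enzyme therefore opens the liver to response, and a fall in a different, normal analyte can supply that response. Bilirubin shows this most clearly. The entry limit of 1.5x ULN lies below the 2x involvement cut, so unless bilirubin rose between screening and baseline it can never be what makes the liver involved, yet it can deliver the PR. SAP 3.8.1 counts a response at any post-baseline assessment, so a single visit is enough.

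The lung floor raises a different question. Where the investigator follows Appendix C and the algorithm follows Appendix B, the two can disagree on the same spirometry. The concordance table would then mix differences between rules with differences between assessors. A lung progression that KARA does not count is also a lack-of-response event missing from KARA DOR.

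**Working it through.** The plan states no figure on this point, so there is none to reproduce. The check applies the rules as written.

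**1. Liver.** Values are multiples of ULN in the order ALT, ALP, bilirubin. Involvement: any analyte above 2. PR: any analyte at or below half its baseline, with no other analyte up by 2 or more. Increase by 2x ULN is read as an increment of 2x ULN. The last column adds the condition that the improving analyte was above 1x ULN at baseline.

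| Baseline | Follow-up | Appendix B as written | With the added condition |
|---|---|---|---|
| 3.0, 1.0, 0.8 | 3.0, 1.0, 0.4 | PR | Unchanged |
| 2.5, 0.9, 0.6 | 3.5, 0.9, 0.3 | PR | Unchanged |
| 0.8, 3.0, 0.5 | 0.4, 3.0, 0.5 | PR | Unchanged |
| 2.8, 1.0, 0.8 | 1.4, 1.0, 0.8 | PR | PR |
| 2.5, 1.8, 0.6 | 2.5, 0.9, 0.6 | PR | PR |
| 0.9, 0.9, 0.8 | 0.9, 0.9, 0.4 | Unchanged | Unchanged |

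In rows 1 to 3 the abnormal analyte has not improved. In row 2 ALT rises by 3.5 - 2.5 = 1.0x ULN, short of the 2x progression limit, and the liver is still PR. Under SAP Table 2 each of these becomes an overall PR if no organ progresses. Row 6 shows that the closing note works when all three analytes are normal. Row 5 matters for the choice of fix: requiring a baseline above 2x ULN, rather than above ULN, would deny PR to an ALP that halves from 1.8x to 0.9x.

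**2. How often chance alone could do this.** The documents give no within-person variation for bilirubin, so this rests on an assumption. Take log-normal noise with standard deviation s = sqrt(ln(1 + CV^2)), independent at baseline and at each of 8 visits, with no true change. At one visit, P(ratio at or below 0.5) = Phi(-ln 2 / (s x sqrt 2)). The any-visit column is simulated.

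| Assumed CV | s | One visit | At least one of 8 visits |
|---|---|---|---|
| 20% | 0.198 | 0.7% | 4% |
| 25% | 0.246 | 2.3% | 12% |
| 30% | 0.294 | 4.7% | 21% |

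These are proportions of participants with KARA liver involvement, a number the documents do not give. They change overall response only where no other organ responds and none progresses.

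**3. Lungs.** With baseline b and follow-up f in % predicted, Appendix C progression is b - f >= 10. KARA progression is b - f >= 10 and f < 75. The rules differ when b - f >= 10 and f >= 75, which requires b >= 75 + 10 = 85. The largest fall scored unchanged is b - 75.

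| Baseline FEV1 | Largest fall scored unchanged |
|---|---|
| 85% | 10 points |
| 90% | 15 points |
| 95% | 20 points |
| 100% | 25 points |
| 110% | 35 points |

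Below a baseline of 85% the two progression rules agree, so they agree for everyone with KARA lung involvement (below 75%). With a response in another organ, a fall from 95% to 76% gives PR in KARA and a mixed response, analysed as progression, under the protocol.

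**4. Rules that work the other way.** FEV1 rising from 78% to 90% is a gain of 12 points and meets the Appendix C lung PR rule. KARA blocks it, because 78% is not involved. ALT falling from 1.8x to 0.8x ULN with the other analytes normal is a liver response under Appendix C, but KARA blocks it because no analyte exceeded 2x ULN.

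**The case against.** The strongest reply is that the liver gap is not peculiar to KARA. Appendix C is at least as open, and KARA is tighter in three respects: the 2x ULN gate, the bar on response in uninvolved organs and the no-worsening clause. That is correct, and it means the liver rule by itself does not separate KARA from the investigator criteria. The gap remains, because an investigator can apply judgement to a loose criterion and a program cannot. *Improvement* could be read to exclude a fall within the normal range, but the SAP does not say so.

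The lung floor can be defended as a prespecified threshold. It equals KARA's own involvement cut, and it affects only lungs that KARA treats as uninvolved both before and after. This stands, and it is why a sensitivity analysis is proposed and not deletion. It does not dispose of the point, since Appendix B says that uninvolved organs can progress and gives no reason for the floor.

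A reader might infer that these rules make KARA ORR too high, or that KARA therefore fails to verify the investigator ORR. The documents support neither. The examples in step 4 lower KARA response, so the net direction is open. No passage gives KARA a verifying or adjudicating role.

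A reader might also object to the joints row, where one P-ROM site up and another down by 1 point meets both PR and progression. Appendix C has the same overlap, and SAP Table 2 already requires no progression in any other organ or site for PR. A tie-break there is a clarification only.

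**Conclusion.** The liver point holds. As written, Appendix B scores PR when a normal analyte halves while the abnormal one is unchanged or rises by less than the progression limit. The lung point holds as a narrower, secondary one: the rules differ only for a baseline of at least 85% with follow-up at or above 75%.

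The consequence is confined to KARA ORR, KARA DOR and the concordance table. The primary investigator-assessed ORR test is unaffected. Neither the size nor the net direction of the effect on KARA ORR can be determined, because the documents give no baseline distribution of liver values or FEV1. The 4% to 21% in step 2 rests on an assumed CV and applies only to participants with liver involvement; it is not an effect on ORR. The row 2 result depends on reading the progression limit as an increment of 2x ULN; rows 1 and 3 do not, since there the abnormal analyte is unchanged.

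**What to change.** In SAP Appendix B:

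- **Liver.** Define KARA liver PR as a 50% decrease in an analyte (ALT, ALP or total bilirubin) that was above ULN at baseline. Keep the no-worsening clause and the organ-involvement gate at 2x ULN.
- **Lungs.** Keep the prespecified rule, state the reason for the 75% floor, and repeat KARA ORR, KARA DOR and the concordance table without the floor as a sensitivity analysis. Disagreement due to the rule can then be told apart from disagreement between assessors.
- **Joints (optional).** State which category applies when both P-ROM criteria are met.

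The cost is a few lines of appendix text, a rerun of the KARA program and one extra set of tables. No new data are needed, and the sample size, alpha and primary analysis do not change.
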